born, clinical symptoms, and other clinical information we designed. After discharge, all the patients received a regular follow up for late complications including respiratory symptoms (including home respiratory support, respiratory medication administration, cough without cold at least once per week, re-hospitalization due to respiratory diseases), vomiting when feeding, hypoxic ischemic injury, retinopathy of prematurity, rehospitalization and sudden death.

Measurements and definitions

Respiratory morbidity included pneumonia, respiratory medication administration for dyspnea, cyanosis and intermittent apnea, and cough without cold at least once per week. Vomiting when feeding referred to vomiting at least once a week and retinopathy of prematurity were diagnosed by local doctors. The diagnoses of hypoxic-ischemic injury mainly depend on MRI.

pH-MII methods

A 24h pH-MII measurement was carried out twice in each infant in the study group of 116 infants with BPD. The first test was performed at 36 weeks PMA and the second, at the last interview between the 17th and 18th month of PMA. Pathological GER was diagnosed when both the tests were positive for GER. In pH-MII monitoring, the probe (Kanglian, Beijing, China) had eight impedance channels (Z1-Z6) and two pH channels. The probe was inserted transnasally into the esophagus. The proximal pH channel was positioned 3 cm above the left diaphragm and the distal pH channel was positioned in the stomach. The position of the pH channels was verified by chest radiography. The data were evaluated using the manufacturer's software and each trace was manually reviewed by the same operator. This operator was not informed of the final outcome.

GER was diagnosed based on the proximal pH channel. Reflux index (RI), which is the percentage of the total recording time with an esophageal pH < 4, was used to categorize pathological GER. Acid GER was defined by a RI > 12, irrespective of the impedance value. Weak acid reflux was defined as a pH between 4–7 when the impedance value decreased > 20% from the baseline while the duration of intragastric pH > 4 for < 70% of the time. DGER was diagnosed for RI < 12 with decreasing impedance and when the intragastric pH > 4 for > 70% of the time. GER without acid GER and DGER was regarded as non GER.

Determination of gastric sodium ions

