The gastric juice was sampled from 89 infants. All medications were forbidden 24 hours prior to sample collection. A feeding tube was always placed for daily meals. Gastric juice was taken for 30 minutes via the feeding tube before meal at 2AM, 10AM and 6PM in a given day with an interval of 8 hours, and was analyzed on a rapid ion analyzer (BHF-II, Bairikang, Beijing). Each patient was sampled three times and a Na⁺ concentration > 50 mmol/L in all three samples was considered positive.

Statistics

Continuous variables were graded as categorical variables and the categorical variables were expressed as frequency and percentage. Chi-square test was used to compare categorical differences. Adjusted odds ratios (ORs) and corresponding 95% confidence intervals (CIs) for every late complication of BPD were estimated separately with multiple logistic regression models (forward). Potential confounders included gender, GA (< 30 weeks and \geq 30 weeks), birth weight (< 1500 g and > 1500 g), Apgar score, invasive ventilation (< 7 days and \geq 7 days), pulmonary surfactant, caffeine, ventilator-associated pneumonia, and GER were

adjusted. All computations relied on standard software (SPSS v19.0; SPSS Inc, Chicago, IL, USA), and statistical significance was set at $P < 0.05$.

Results

Prevalence of Late Complications

Among the 116 infants with BPD in the final cohort, late complications occurred in 74 infants with an overall prevalence of 63.79%. These complications included respiratory symptoms in 49.14% (n=57) infants, including pneumonia (n=10, 8.62%); dyspnea, cyanosis and intermittent apnea warranting respiratory medication administration (n=25, 21.55%), and cough (n=44, 37.93%). Vomiting occurred in 45 (38.79%), ROP in 30 (25.86%), and hypoxic-ischemic injury in 4 (3.45%) infants. One (0.86%) infant suffered sudden infant death syndrome. Re-hospitalization was recorded in 31 (26.72%) infants.

GER Prevalence in BPD

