Pathological GER occurred in 49 infants with BPD with an overall prevalence of 42.24%, including acid GER (n=21, 18.10%) and DGER (n=28, 24.14%). SI, SSI, and SAP measurements were $> 99\%$ in all 49 infants, confirming the association between reflux events and symptoms. Weak acid GER was found in almost all infants including those with acid GER, DGER and non GER. The percentage of weak acid GER events over the overall reflux episodes varied from 40.74–100%, and there was no significant difference among infants with acid GER, DGER and non GER. In the evaluation of DGER, 33 infants are positive for pH-MII monitoring, and gastric $\text{Na}^+ > 50$ mmol/L was noted in 28 infants who were finally diagnosed as DGER. Five infants positive for pH-MII and negative for gastric $\text{Na}^+ > 50$ mmol/L were diagnosed as weak acid GER. No infants negative for pH-MII and positive for

gastric $\text{Na}^+ > 50 \text{ mmol/L}$ were noted. Among the BPD infants, the prevalence of acid GER and DGER was 12% and 17.33% in mild BPD, 32.14% and 32.14% in moderate BPD, and 23.08% and 46.15% in severe BPD individually. Among the 74 symptomatic infants, the prevalence was 14.66% and 21.55%.

Risk Factors for Late Complications

Accordingly, risk factors for respiratory symptoms were $\text{GA} \leq 30$ weeks (odds ratio, OR=3.213; 95% CI, 1.221-8.460), birth weight $< 1500 \text{ g}$ (OR=2.803; 95% CI, 1.014-7.749), invasive ventilation > 7 days (OR=4.952; 95% CI, 1.508-16.267), acid GER (OR=4.630; 95% CI, 1.305-16.420), and DGER (OR=5.588; 95% CI, 1.770-17.648). Risk factors for vomiting were $\text{GA} \leq 30$ weeks (OR=5.813; 95% CI, 2.424-13.940), acid GER (OR=3.394; 95% CI, 1.107-10.403), and DGER (OR=4.379; 95% CI, 1.552-12.354). Risk factors for ROP were $\text{GA} \leq 30$ weeks (OR=8.741; 95% CI, 3.203-23.851), while the major risk factors for re-hospitalization were $\text{GA} \leq 30$ weeks (OR=3.894; 95% CI, 1.405-10.791), acid GER (OR=5.866; 95% CI, 1.640-20.972), and DGER (OR=8.436; 95% CI, 2.697-26.382).

Conclusion

In summary, the prevalence of late complications of BPD is high; pediatricians should pay great attention to BPD infants after discharge to reduce the damage caused by these late complications. GER, or rather DGER, is a potential risk for the late complications of BPD.

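### The GER exposure requires a second positive pH-MII test, done after late complications had begun to accrue, so infants positive only at 36 weeks PMA fall in the non-GER reference group

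*Combined protocol and SAP*

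**What the plan says.** The pH-MII methods section states: "A 24h pH-MII measurement was carried out twice in each infant in the study group of 116 infants with BPD". The first test is at 36 weeks PMA and "the second, at the last interview between the 17th and 18th month of PMA". The rule that combines them is: "Pathological GER was diagnosed when both the tests were positive for GER". Infants who are neither acid GER nor DGER are classed as non GER; there is no fourth category.

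On outcomes, the Patients section says: "After discharge, all the patients received a regular follow up for late complications". The Research background gives the schedule as monthly visits over 18 months from discharge.

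GER then enters a separate forward logistic model for each late complication (Statistics). The other listed adjustment variables are demographic, birth and neonatal-care factors.

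DGER status also used gastric sodium. Under Determination of gastric sodium ions: "The gastric juice was sampled from 89 infants", with no date relative to either pH-MII test. The Results give 33 infants meeting the pH-MII criterion for DGER, of whom 28 were confirmed by sodium. The remainder are described as "Five infants positive for pH-MII and negative for gastric" sodium above the threshold, and were reclassified as weak acid GER.

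**The concern.** A prospective cohort analysis of a risk factor needs the exposure fixed before the outcome period starts. Here half of the definition is measured at the end of that period. An infant who is positive at 36 weeks becomes exposed only if GER is still present at the last interview, and respiratory illness, its treatment or death in between could affect that.

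All 49 exposed infants were positive at 36 weeks PMA, so GER at that time does precede post-discharge follow-up. What is not shown is that persistent GER, the exposure actually modelled, preceded the complications.

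The error could run either way. If complications help to keep GER going, the odds ratios are inflated. If GER that later resolved also did harm, those infants raise the reference-group risk and the odds ratios are diluted. The Conclusion that GER, and DGER in particular, is a potential risk rests on these odds ratios.

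**Working it through.** **1. Timing.** At 4.348 weeks per month, 17 months PMA is 73.9 weeks and 18 months is 78.3 weeks, so the second test is about 38 to 42 weeks after the first. If the last interview is instead the end of 18 months' follow-up from discharge, and discharge is at or after 36 weeks PMA (assumed), it falls at 36 + 78.3 = 114.3 weeks PMA or later. On either reading it comes after complications began to accrue.

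**2. Where discordant infants go.** The stated prevalence reproduces: 21 acid GER + 28 DGER = 49, and 49/116 = 42.24%. The severity percentages back-solve to:

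| BPD | N | Acid GER | DGER |
|---|---|---|---|
| Mild | 75 | 9 (12%) | 13 (17.33%) |
| Moderate | 28 | 9 (32.14%) | 9 (32.14%) |
| Severe | 13 | 3 (23.08%) | 6 (46.15%) |
| Total | 116 | 21 | 28 |

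No infant was set aside. Given the both-positive rule, any infant positive at one test only must be among the 116 − 49 = 67 non GER. The text does not say so; this is an inference from the rule and the counts.

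**3. Crude table for any late complication.** GER Prevalence in BPD says: "Among the 74 symptomatic infants, the prevalence was 14.66% and 21.55" percent. On 74 these give 10.85 and 15.95 infants, which are not whole numbers. On 116 they are exactly 17 and 25, so I read them as 17/116 and 25/116.

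| | Complication | None | Total |
|---|---|---|---|
| GER | 42 | 7 | 49 |
| Non GER | 32 | 35 | 67 |
| Total | 74 | 42 | 116 |

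OR = (42 × 35)/(32 × 7) = 6.56, Wald 95% CI 2.58 to 16.68.

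**4. Reclassifying by the first test.** Suppose k of the 67 were positive at the first test only (k is assumed). If e of them had complications,

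OR = (42 + e)(35 − k + e) / [(32 − e)(7 + k − e)].

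| k | e = 0 | e = k × 32/67 (reference-group risk) | e = k |
|---|---|---|---|
| 5 | 3.28 (1.46–7.39) | 5.05 | 8.70 (3.40–22.27) |
| 10 | 1.93 (0.89–4.16) | 4.19 (1.85–9.47) | 11.82 (4.56–30.63) |
| 15 | 1.19 (0.56–2.55) | 3.62 (1.64–8.03) | 16.76 (6.32–44.48) |

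At k = 10 the odds ratio is 6.27 with e = 7 and 7.64 with e = 8, so the move is downward if seven or fewer had complications and upward if eight or more did.

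**5. Can the definition create an association by itself?** Assume 60% are positive at the first test, unrelated to outcome, and that the chance of remaining positive is a in infants with complications and b in those without. Then

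OR = [0.6a/(1 − 0.6a)] / [0.6b/(1 − 0.6b)].

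| Persistence with / without complications | OR | Reversed |
|---|---|---|
| 70% / 70% | 1.00 | 1.00 |
| 70% / 60% | 1.29 | 0.78 |
| 80% / 60% | 1.64 | 0.61 |
| 90% / 50% | 2.74 | 0.37 |

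For 80%/60%: (0.48/0.52)/(0.36/0.64) = 1.64. A non-null odds ratio appears although 36-week GER has no effect.

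**6. Smaller items.** Counting the five sodium-negative infants as DGER is the k = 5 row: 3.28 to 8.70. For the one death, moving the infant from unexposed to exposed gives (43 × 35)/(31 × 7) = 6.94, and dropping the infant from the unexposed group gives (42 × 35)/(31 × 7) = 6.77.

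**The case against.** No discordant infant is reported, so k could be zero. The ends of the range in step 4 assume that all or none of the reclassified infants had complications; at the reference group's own risk the association shrinks but its interval excludes 1 for k = 10 and 15. In the null example the most extreme case shown, 2.74, is below every reported GER point estimate, and its 60% starting prevalence (about 70 infants) implies roughly 17 to 23 discordant infants, more than the k of 5 to 15 used elsewhere. The crude composite is not one of the modelled outcomes, and it includes ROP, for which GER is not listed as a risk factor. Requiring two positive tests is a defensible way to identify persistent GER, and the trace reader was blinded to final outcome. Changing the primary exposure after results are known is itself post hoc.

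Most of this stands as a limit on magnitude: the calculations show what could happen, not what did, and they do not predict how the adjusted odds ratios would move. It does not answer the design point. Blinding prevents biased reading of a trace but does not stop events in follow-up from affecting whether reflux persists. Adjustment for birth and neonatal factors cannot restore time order. The post hoc objection is best met by reporting both definitions side by side and saying when each was chosen.

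**Conclusion.** The concern holds. The modelled exposure uses information from after outcome collection began, and by the counts the reference group must contain any infant whose GER was present at 36 weeks and later resolved. Neither the size nor the direction of the effect on the reported odds ratios can be computed, because first-test results and the number of discordant infants are not given. The illustrative ranges rest on an assumed k, on reading the 14.66% and 21.55% as shares of 116, and on an unadjusted composite outcome. As reported, the analysis supports an association between persistent GER and late complications. It does not test GER fixed before follow-up as a risk factor, and this should be put right before the Conclusion is relied on.

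**What to change.** - Make the 36-week PMA pH-MII result (acid GER, DGER or neither) the primary exposure in the logistic models, for every infant with that test, including the infant who died and any without a second test.
- Report the two tests separately in a 3 × 3 table by type, and state how type was assigned when they disagreed.
- Keep the two-test definition as a secondary analysis, described as an association with persistent GER.
- State when gastric sodium was sampled. Use it for DGER in the primary definition only if it was taken at the first test; otherwise classify DGER by the first pH-MII test and add a sodium-confirmed sensitivity analysis.
- Reconcile two tests in each of 116 infants with the statement "One (0.86%) infant suffered sudden infant death syndrome" (its timing is not given), and 17 to 18 months PMA with 18 months of follow-up after discharge.

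The cost is small: first-test data exist, so the work is to reclassify infants, check the sodium sampling dates and refit the same models. The downside is that one test classifies less strictly than two, so the odds ratios may change or attenuate.

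### An all-three-samples sodium rule that the DGER definition does not mention places five pH-MII-positive infants in the non-GER reference group, and the effect on the odds ratios is not shown

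*Combined protocol and SAP*

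**What the plan says.** Three sections bear on this, all in the combined protocol and SAP.

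- **pH-MII methods.** "DGER was diagnosed for RI < 12 with decreasing impedance and when the intragastric pH > 4 for > 70% of the time". Sodium is not mentioned. Weak acid reflux is limited to intragastric pH above 4 for less than 70% of the time. The section closes with "GER without acid GER and DGER was regarded as non GER".
- **Determination of gastric sodium ions.** "The gastric juice was sampled from 89 infants". The sampling was: "Gastric juice was taken for 30 minutes via the feeding tube before meal at 2AM, 10AM and 6PM in a given day". Sodium above 50 "mmol/L in all three samples was considered positive". The section gives no reason for requiring all three and does not link the result to the DGER definition.
- **GER Prevalence in BPD (Results).** In the evaluation of DGER, "33 infants are positive for pH-MII monitoring", and 28 of them with positive sodium became the final DGER group. "Five infants positive for pH-MII and negative for gastric" sodium above the cut-off were called weak acid GER.

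**The concern.** The final DGER class depends on a second test that the definition of DGER leaves out. Five infants who passed the defining test were moved by the second one into the comparison group for every GER odds ratio. They carry a label, weak acid GER, whose own pH condition is the opposite of the one they were reported to meet.

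The way the three samples are combined adds to this. If all three must exceed the cut-off, one low sample outweighs two high ones, so an infant with genuine DGER can fail by chance. The Conclusion singles out DGER. With 28 DGER infants and 67 reference infants, the placement of five matters, and no analysis shows how much.

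**Working it through.** **1. Reproduce the stated counts.** The Results give 116 infants, 21 acid GER, 33 pH-MII positive for DGER and 5 of those sodium negative.
- DGER: 33 − 5 = 28; 28/116 = 24.14%, as printed.
- Pathological GER: (21 + 28)/116 = 49/116 = 42.24%, as printed.
- Non-GER reference: 116 − 49 = 67. The five are 5/33 = 15.2% of the pH-MII positives and 5/67 = 7.5% of the reference.
- If the five counted as DGER: 33/116 = 28.45%, GER 54/116 = 46.55%, reference 62.

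**2. Compare the definitions.** An infant positive on the DGER pH rule has intragastric pH above 4 for more than 70% of the time. Weak acid reflux requires less than 70%. If pH-MII positive in the Results means positive on the Methods rule, the five cannot meet the weak acid definition.

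**3. Chance of failing an all-three rule.** Let p be the probability that one sample exceeds 50 mmol/L in a true DGER infant. The documents do not give p, so it is an assumption with a range. With independent samples, P(3 of 3) = p³ and P(at least 2 of 3) = p³ + 3p²(1 − p).

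| p | 3 of 3 | at least 2 of 3 |
|---|---|---|
| 0.70 | 34.3% | 78.4% |
| 0.80 | 51.2% | 89.6% |
| 0.90 | 72.9% | 97.2% |
| 0.95 | 85.7% | 99.3% |

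Correlation between an infant's samples raises the pass rate. In a beta-binomial model at p = 0.70 and correlation 0.5, P(3 of 3) is 53.6%.

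The observed pass rate is 28/33 = 84.8% (exact 95% CI 68.1% to 94.9%). If all 33 truly had DGER and samples were independent, p = (28/33)^(1/3) = 0.947 (0.880 to 0.983). At p = 0.70, 33 × (1 − 0.343) = 21.7 failures would be expected; five occurred.

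**4. Effect on vomiting.** Counts by GER class are not printed. They can be recovered if the final model contains only the three printed terms (GA, acid GER, DGER). Given 21/28/67 infants and 45 events, one table was found that fits: GA ≤ 30 weeks in 10/21 acid GER, 18/28 DGER and 23/67 non GER; vomiting in 11, 18 and 16; 32 of the 45 events at GA ≤ 30 weeks. Refitting returns 5.813, 3.394 and 4.379 with the printed intervals.

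The five were then moved to DGER and the model refitted for each of 6 × 6 = 36 splits (0 to 5 at GA ≤ 30 weeks, 0 to 5 vomiting).
- Lowest DGER OR: 1.930 (0.715 to 5.209), with none vomiting and all at GA ≤ 30 weeks.
- Highest: 12.80 (4.095 to 40.02), with all vomiting and none at GA ≤ 30 weeks.
- The DGER lower limit is below 1 in 5 splits: none vomiting with two to five at GA ≤ 30 weeks, and one vomiting with all five at GA ≤ 30 weeks.
- The acid GER lower limit runs from 0.88 to 1.74, against 1.107 printed.

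**5. Cruder check, any late complication.** The printed 14.66% and 21.55% match 17/116 and 25/116 and no whole number out of 74. Taking them so, the reference has 74 − 17 − 25 = 32 symptomatic infants.
- As classified: (25 × 35)/(3 × 32) = 9.11 (2.51 to 33.11).
- Five moved to DGER: from (25 × 30)/(8 × 32) = 2.93 (1.15 to 7.49) to (30 × 35)/(3 × 27) = 12.96 (3.57 to 47.03).
- Five excluded: from (25 × 30)/(3 × 32) = 7.81 to (25 × 35)/(3 × 27) = 10.80.

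**The case against.** A strict confirmatory test is a legitimate design choice, and the five may be pH-MII false positives that sodium rightly removed. No sample values are reported, so they may have had no high sample or only one. This stands: the documents cannot show that any of them is a sampling miss.

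A reader might infer that three of three is stricter than the study's own 70% rule and that two of three would match it. The documents do not support this. The 70% is time with intragastric pH above 4. The sodium rule is a concentration in three timed collections, and nothing links the two. As a plain count, two of three is 66.7%, which is not above 70%. The 34% and 51% pass rates also lie below the exact interval for 28/33, so they do not describe these 33 infants if all truly had DGER.

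The threat to the DGER result is also limited. If the five vomited like other DGER infants (18/28), 5 × 18/28 = 3.2 would be expected to vomit, and the chance of none is (10/28)^5 = 0.6%. With three vomiting, the DGER OR is 4.20 to 6.89 with lower limits of 1.53 to 2.41. This holds only if they resemble DGER infants. If they were a random draw from the 67 reference infants, 51 of whom did not vomit, the chance of none is (51·50·49·48·47)/(67·66·65·64·63) = 24%. Their outcomes are not reported, so neither case can be excluded.

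**Conclusion.** The point holds as a definitional conflict with an untested consequence. The sections disagree on whether sodium is part of DGER and on what the five should be called, and the five make up 7.5% of the reference group.

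A reader might go further and infer that true DGER infants were lost and the DGER odds ratio is therefore too low, or that the DGER conclusion is wrong. Neither follows. The odds ratio can move either way, and for vomiting DGER keeps a lower limit above 1 in 31 of 36 splits. Acid GER, with a printed lower limit of 1.107, has less room.

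The vomiting figures rest on the recovered table and a three-term model. The splits are possibilities and are not equally likely. The any-complication figures are unadjusted and rest on reading two percentages as fractions of 116. Adjusted effects on respiratory symptoms and re-hospitalization could not be checked.

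**What to change.** - Reconcile the pH-MII, sodium and GER prevalence sections: say whether sodium is part of the DGER definition, why all three samples are required, and which class applies to an infant positive on pH-MII and negative on sodium.
- Keep the all-three rule as the primary classification. Replacing it with two of three now would be a post hoc choice made with results known.
- For each of the five, report how many of the three samples exceeded 50 mmol/L.
- Rerun all models with the five as non GER, as DGER, and excluded. If the individual values are on file, which the documents do not state, add two of three as a sensitivity rule only.
- Report DGER and acid GER odds ratios with intervals for each version, and qualify the DGER statement in the Conclusion if it does not hold throughout.

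The cost is a few sentences in Methods, a small amount of reanalysis and possibly a less firm conclusion. The scope is bounded: the Results require both tests for DGER, so only these five infants can change class.

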Brief Title: GER Poses a Potential Risk for Late Complications of BPD

Official Title: Gastroesophageal Reflux Really Pose a Potential Risk for Late Complications of Bronchopulmonary Dysplasia in Extremely Premature Infants

Identifiers: NCT03014453

Unique Protocol ID: A333-1

Sponsor: Shengjing Hospital

Investigator: [name]

Official Title: Professor

Affiliation: Shengjing Hospital

Study Start: July 1, 2017

Document Date: March 24, 2020

Study Protocol

Research background

Bronchopulmonary dysplasia (BPD) is a common condition in the low birth weight infants. Although most of the BPD symptoms improved after a regular treatment in infancy, there are still a few late complications left such as the frequent respiratory symptoms, a slower weight gain and even sudden death. These late complications have made so much trouble to the healthcare of BPD infants. How to find the risk factors and to reduce the prevalence of these late symptoms becomes necessary. In this study, a cohort of BPD infants was observed with the late complications obtained by a monthly followed up for 18 months after discharge, the prevalence and risk factors were analyzed via logistic regression, calculating odd ratios (OR) and 95% confidence intervals. As one of the risk factors, GER was verified whether to play a critical role in these late complications.

Research purposes

A prospective cohort study is carried out to explore the potential risk of gastroesophageal reflux as a late complication of bronchopulmonary dysplasia in preterm infants.

Methods

Patients

The study was approved by the Ethics Committee of China Medical University. Written consent was obtained from the parents. The cohort included infants born at or before 32 weeks gestational age (GA) with BPD between January 2017 and July 2018 at Shengjing Hospital of China Medical University, the First Hospital of Jilin University, and Shanghai General Hospital of Shanghai Jiao Tong University. BPD was diagnosed at 36 weeks postmenstrual age (PMA) on the National Heart, Lung and Blood Institute classification and categorized as “mild, moderate or severe”. Infants with no BPD, severe gastrointestinal malformations and refused GER monitoring were excluded.

Detailed information on the BPD infants, including age, sex, Apgar scores, treatments after

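### Forward selection leaves GER, the exposure under study, out of the ROP model and leaves the vomiting GER odds ratios adjusted for gestational age only, although Statistics says nine factors were adjusted

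*Combined protocol and SAP*

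**What the plan says.** The Research background makes GER the factor of interest: "GER was verified whether to play a critical role in these late complications". Under Methods, Statistics, the adjusted ORs for each complication "were estimated separately with multiple logistic regression models (forward"). The next sentence lists gender, GA, birth weight, Apgar score, invasive ventilation, surfactant and caffeine, ends "ventilator-associated pneumonia, and GER were", and continues with the word adjusted. No entry or removal threshold is given.

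Under Results, Prevalence of Late Complications, the event counts are "Vomiting occurred in 45 (38.79%), ROP in 30 (25.86"%), and "Re-hospitalization was recorded in 31 (26.72%) infants". Respiratory symptoms occurred in 57 of the 116 infants. The exposure groups, under GER Prevalence in BPD, are "including acid GER (n=21, 18.10%) and DGER (n=28, 24.14"%), which leaves 116 - 49 = 67 without pathological GER.

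Under Risk Factors for Late Complications, vomiting has three factors, with GA at or below 30 "weeks (OR=5.813; 95% CI, 2.424-13.940), acid GER (OR=3.394; 95% CI, 1.107-10.403), and DGER (OR=4.379; 95% CI, 1.552-12.354"). ROP has GA alone: "weeks (OR=8.741; 95% CI, 3.203-23.851), while the major risk factors for re-hospitalization were" GA, acid GER and DGER. The covariates kept in each model are not listed.

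**The concern.** Forward selection keeps only terms that pass an entry test. A model built that way need not contain GER, and need not contain any particular confounder. It cannot also be a model in which all nine factors were adjusted.

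Three things follow.

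- An outcome for which GER is not selected has no estimate for the study's own exposure, and that gap cannot be read as no association.
- GER ORs for different outcomes carry different adjustment sets, so they cannot be compared, and some may retain confounding by factors that were measured.
- Reporting GER only when it is selected tends to overstate modest effects and makes the Wald intervals too optimistic.

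The Conclusion, which names DGER as a potential risk, rests on these ORs.

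**Working it through.** **Inputs.** N = 116; events: vomiting 45, ROP 30, re-hospitalization 31, respiratory 57; acid GER 21, DGER 28, none 67; the ORs and CIs under Risk Factors for Late Complications. Standard errors come from SE = ln(upper/lower)/3.92. The cell counts below are reconstructed, not printed in the document.

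**1. ROP.** With 30 events and 86 non-events and no empty cell there are 29 × 85 = 2465 possible 2x2 tables. Only one returns the reported figures, 24/51 in the lower-GA group against 6/65 in the other:

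- OR = (24 × 59)/(27 × 6) = 1416/162 = 8.741
- SE = √(1/24 + 1/27 + 1/6 + 1/59) = 0.5122
- 95% CI = exp(2.168 ± 1.96 × 0.5122) = 3.203 to 23.851

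This is a crude OR. No other term was in the model.

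**2. Vomiting.** In a maximum-likelihood logistic model the fitted event totals in each covariate group equal the observed ones, so they must be whole numbers. For each way of placing infants of the three GER groups in the lower-GA group (43,314 layouts, 5 to 111 infants in total), the reported ORs were held fixed, the intercept was set so that fitted events summed to 45, and the group totals and SEs were read off.

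Only one layout gives whole-number totals with matching SEs: lower GA in 23/67 none, 10/21 acid and 18/28 DGER. The intercept is -1.940.

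| Term | Fitted events | SE from layout | SE from reported CI |
|---|---|---|---|
| Lower GA | 32.000 | 0.4463 | 0.4463 |
| Acid GER | 11.000 | 0.5715 | 0.5715 |
| DGER | 18.000 | 0.5291 | 0.5292 |

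The largest departure from a whole number is 0.0003. Refitting with 32, 11 and 18 returns all nine reported numbers. The lower-GA group totals 23 + 10 + 18 = 51, the same 51 found separately from ROP.

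Crude vomiting counts are 11/21 acid, 18/28 DGER and 45 - 11 - 18 = 16/67 none. Crude ORs are (11/10)/(16/51) = 3.51 and (18/10)/(16/51) = 5.74. Adjusting for GA gives 3.39 and 4.38.

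**3. Re-hospitalization.** On the recovered layout a GA + GER model implies totals of 22.20, 8.70 and 15.38, which are not whole numbers, and SEs of 0.500, 0.623 and 0.574 against 0.520, 0.650 and 0.582 from the reported CIs. No other layout fits, nor does removing one infant. An unlisted term is likely.

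**4. Respiratory symptoms.** GA, birth weight and ventilation are reported with GER. The other five confounders are not shown.

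**5. What non-entry of GER allows for ROP.** Assume entry at 0.05 by a 2-df score test given GA, the recovered layout, and at least one ROP event in each GER group. GA-adjusted ORs compatible with non-entry then run from about 0.14 to 3.8 (acid) and 0.22 to 3.5 (DGER). For example, ROP in 8/21, 12/28 and 10/67 gives 3.3 (0.97-11.3) and 2.9 (0.97-8.7), p = 0.06. With a true OR of 2 or 3 for both types, GER would fail to enter in 74% or 45% of data sets.

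**6. Possible effect of an omitted confounder on vomiting (hypothetical).** Take a two-level factor that just misses entry and is spread over the GER groups as GA is (34% none, 48% acid, 64% DGER). With OR 2.45, DGER moves from 4.4 to 3.5 (1.2-10.3) and acid GER from 3.4 to 3.1 (1.0-9.9). Acting the other way (OR 0.38), it gives 6.3 and 4.1. With a milder spread (40/45/50%) the ranges are 4.2-5.1 and 3.4-3.7.

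**7. Selection effect.** Treat GER as a 2-df block and divide the bivariate normal likelihood by the probability that a noncentral chi-square exceeds 5.99, with the acid/DGER correlation assumed at 0.2-0.5 (0.31 in the vomiting reconstruction).

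| Outcome | Acid GER | DGER |
|---|---|---|
| Respiratory | 4.6 to 3.4-4.0 | 5.6 to 4.0-4.7 |
| Vomiting | 3.4 to 2.4-2.8 | 4.4 to 2.9-3.5 |
| Re-hospitalization | 5.9 to 5.4-5.7 | 8.4 to 7.7-8.1 |

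**8. Room for a full model.** Eight confounders (Apgar taken as two levels) plus two GER terms make 10 parameters. Events per parameter are 57/10 = 5.7, 45/10 = 4.5, 31/10 = 3.1 and 30/10 = 3.0. With five parameters they are 11.4, 9.0, 6.2 and 6.0.

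**The case against.** Screening several risk factors is also a stated aim, GER is introduced as one of them, and forward selection is a known, if weak, tool for that. The method is disclosed, the sentence on adjustment is ungrammatical and may mean that the factors were offered to selection, and the different factor lists by outcome hint that the models differ. This softens the point. It does not remove it: the title and purpose centre on GER, and nothing tells the reader that one OR is crude and others are adjusted for GA alone.

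The sizes in steps 5 to 7 are fair targets.

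- The ROP example lies near the upper edge of what non-entry allows; protective ORs fit as well. The miss rates mainly reflect 30 events, so forcing GER in would yield a reported interval rather than more power.
- The omitted-confounder case is a chosen extreme. Part of its upward shift is non-collapsibility: a factor equally common in all groups would still raise the ORs to about 4.6 and 3.6.
- The selection figures rest on an unstated entry rule and assumed correlations. Joint GER p-values are at most 0.014 for all three outcomes.
- For re-hospitalization, several missing infants or a misprint are not excluded.

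These objections limit the magnitudes. The ROP and vomiting reconstructions stand.

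**Conclusion.** The concern holds. The ROP OR labelled adjusted is crude, and the vomiting GER ORs are adjusted for GA only, contrary to the Statistics section. Confidence in this is high, because two separate reconstructions match the reported figures and agree on 51 lower-GA infants. That re-hospitalization has an unlisted term is likely, not proven.

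The GER effect on ROP is unreported and could lie in either direction. The fully adjusted vomiting ORs cannot be computed from the document; the shifts shown are illustrations that depend on an assumed 0.05 entry level and an assumed confounder spread. Shrinkage for selection would be moderate and is smallest for re-hospitalization. The conclusion that DGER is a potential risk is not overturned, but its supporting ORs need relabelling and a consistent model.

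**What to change.** Replace forward selection with one fixed logistic model for respiratory symptoms, vomiting, re-hospitalization and ROP. Force in GER (acid, DGER, none) and the same confounders each time. Either use all eight listed confounders with Firth penalisation, or a shorter set chosen on clinical grounds, not from the forward results, and written down before the re-run. List the covariates in each model and report the GER ORs and CIs for all four outcomes whether or not significant. As results are known, declare this a revised, post hoc analysis and show the forward results beside it. Leave hypoxic-ischemic injury (4 events) and sudden death (1) as counts.

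Until then, label the ROP OR as crude and the vomiting ORs as adjusted for GA and GER only. This needs no new analysis.

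The cost is four re-runs on existing data, one changed sentence and one table. Expect wider intervals, possibly less extreme ORs, and the post hoc label. On the reconstructed vomiting model, Firth penalisation moves acid GER only from 3.39 to 3.26 and DGER from 4.38 to 4.17. Its effect in the 10-parameter model cannot be checked without the data.
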